5.7.2.6. Adverse Events of Special Interest

The AESI for this study is TEs, which are adjudicated by EAC blinded to treatment. The number and percentage of participants with adjudicated TEs and the number of TEs in each treatment group and total will be summarized by SOC and PT.

Among participants with TEs, the number and percentage of participants in each treatment group will be summarized for the following categories:

- Did not use anticoagulants
- Used anticoagulants before the first TE
- Used anticoagulants after the first TE

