- For start date: If the day is missing, then impute with 01, and if both the day and the month are missing, then impute with 01-Jan.
- For end date: If the day is missing, then impute with the last day of that month, and if both the day and the month are missing, then impute with the last visit/contact/survival/death day of study or Day 30.
- If the year is missing, then keep as is. No imputation is required if the complete date is missing.

Definition of Baseline Values

Baseline is defined as the most recent nonmissing assessment within the protocol-defined visit window prior to randomization. If there is no assessment within the visit window of randomization, then the assessment closest to randomization prior to treatment will be used as baseline. Data that are outside the baseline assessment windows specified above will not be excluded from analyses but will be identified as protocol deviations.

Start of Study Treatment

For and exampt treatment group, the start of study treatment will be the start of and exampt. For the UC treatment group, the start of study treatment will be the start of the specific UC drug received by the participant, or if the UC consists of no treatment, then the start of study treatment will be the randomization date for the participant.

Restart of Anticoagulants

The time when anticoagulants were restarted is defined as (date restart anticoagulation - date of the first study treatment) + 1. If the participant is assigned to UC and receive no treatment, then the date of the first study treatment will be replaced by the date of randomization. Oral anticoagulants will be summarized separately.

Study Day

For participants who are randomized to UC group and received no treatment, the study day is calculated based on randomization date. For events prior to randomization, the study day is calculated as date of event - date of randomization; for events on or after randomization, the study day is calculated as date of event - date of randomization + 1. For other participants, the study day is calculated based on the date of treatment initiation, using the same formula as above. Study day is referred as "day" in outputs.

Calculation of On Treatment Nadir

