On treatment nadir is the minimum anti-fXa activity post-randomization (ie, value observed at either 1- or 2-hour post-randomization evaluation). A percent reduction will be calculated as the ratio between the maximum reduction from baseline and the baseline value, multiplied by 100.

Length of Hospitalization and Rehospitalization

The following steps will be followed to calculate the length of hospitalization (or rehospitalization):

- The length of stay (LOS) will be calculated as discharge date/time admission date/time + 1.
- If the participant admission time and the discharge time are missing and the dates are the same, the LOS will be assumed to be 1 day.
- If the participant admission time and the discharge time are missing and the dates are not the same, the LOS will be calculated using the date portion of the dates plus 1.
- If the discharge date is missing and there is no new admission date, the date of the 30-day visit or the date of death (whichever is earlier) will be imputed as the discharge date.
- If the participant has withdrawn consent, the discharge date will be imputed as the date of the 30-day visit or the date of death (whichever is earlier and/or available).

Neurologic Deterioration at 24 hours

Neurologic deterioration at 24 hours is defined as an NIHSS increase \geq 4 at 24 hours compared to baseline or a GCS score decrease \geq 2 at 24 hours compared to baseline.

Neurologic Deterioration at 12 hours

Neurologic deterioration at 12 hours is defined as an increase of \geq 7 point from baseline to 12 hours in NIHSS.

Utility-Weighted mRS

Mean utility values will be based on EQ-5D-5L at the same visit and will be determined by averaging the utilities of all participants within each mRS category.

AEs With Partial or Missing Start and End Date

If the start date of an AE is partially or completely missing and the end (stop) date and time of the AE do not indicate that it occurred prior to the first dose, then the determination of treatmentemergent status will be based on the following:

- If the start year is after the year of the first dose, then the AE is treatment emergent.
- If the start year is the same as the year of the first dose and:
 - If the start month is missing, then the AE is treatment emergent.
 - If the start month is present and is the same as or after the month of the first dose, then the AE is treatment emergent.

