Page 41 of 52 Alexion Confidential • If the start date is completely missing, then the AE is treatment emergent.

If both start and end dates of AEs are completely missing, no imputation will be performed, and those AEs will be considered treatment emergent.

If the start date is partial:

- 1. If only the day is missing:
 - a. If the month/year of the start date is the same as those of the first study drug administration date, then the missing day will be imputed as the smaller nonmissing value of (day of first study drug administration, day of the AE end date).
 - b. Otherwise, impute the missing day as "01."
- 2. If both day and month are missing:
 - a. If the year of the AE start date coincides with the year of the first study drug administration date, the partial start date will be set as the first study drug date. If this leads to a date after the AE end date, then the missing day and month of the AE start date will be imputed as the day and month of the AE end date.
 - b. If the year of the AE start date is different from the year of the first study drug administration date, the missing day and month of the AE start date will be imputed as "01" and "01."

If the start date of an AE is the same as the first study drug administration date but the time is missing, the AE is treatment-emergent.

If the stop date is partial:

- 1. If only the day is missing:
 - a. The missing day will be imputed as the last of the month, adjusting for the leap year.
- 2. If both day and month are missing:
 - a. If the year of the AE end date coincides with the maximum of (the year of first study drug administration date or the year of the last study drug administration), then the missing month will be imputed as the month of the corresponding study drug administration date (first or last) and the missing day will be imputed as the last of the month adjusting for the leap year.
 - b. Otherwise, the missing day and month of the AE stop date will be imputed as "31" and "12."

Adverse Event of Special Interest (AESI)

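### Two partial-date rules in SAP 6.1 can date a post-treatment adverse event, and if applied to restarts an anticoagulant restart, before treatment began

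*SAP*

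**What the plan says.** All the rules are in SAP Section 6.1.

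- **AE start, only the day missing (item 1 of the partial start date list).** Item 1a applies when the recorded month and year are those of the first dose: "the missing day will be imputed as the smaller nonmissing value of (day of first study drug administration, day of the AE end date". Item 1b covers any other month: "Otherwise, impute the missing day as" 01.
- **AE start, day and month missing (item 2a).** In the dosing year the start is set to the first study drug date. A correction follows: "If this leads to a date after the AE end date", the day and month of the end date are used instead.
- **Treatment-emergent status** is decided separately, at month level: "If the start month is present and is the same as or after the month of the first dose", the event counts as treatment-emergent.
- **Concomitant medication start.** "For start date: If the day is missing, then impute with 01, and if both the day and the month are missing", 1 January is used. These imputations come after the prior/concomitant flag has been set.
- **Restart of anticoagulants.** "The time when anticoagulants were restarted is defined as (date restart anticoagulation - date of the first study treatment) + 1". This paragraph gives no rule for a partial restart date.

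**The concern.** Item 1a appears designed to stop an imputed start from falling after the end of the event. Taking the smaller day number does that when start and end lie in the same month. When the event ends in a later month, the end day says nothing about the start month, and a small end day pulls the onset to before dosing. Item 2a, for the less complete record, does compare dates, so the record with more information can receive the worse onset.

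The medication rule has a different gap. It fills in the first of the month, or of the year, without checking that the result is on or after treatment start. That is harmless for a drug whose start date only goes into a listing. A restart after treatment, however, cannot have a date before treatment, and the restart variable subtracts the treatment date directly.

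At stake are the credibility of AE onset days and durations, and of time to anticoagulant restart, in a trial whose only AE of special interest is thrombotic events.

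**Working it through.** The plan states no figure on this point. The check applies the rules literally, with study treatment on 20 March 2022.

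**AE start recorded as March 2022, day missing.** Under item 1a the imputed day is min(day of first dose, day of AE end). Under the SAP's study-day rule, an event before treatment has study day = event date - treatment date; on or after treatment, 1 is added.

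| AE end | Item 1a | Study day | Earlier of the two full dates |
|---|---|---|---|
| missing | 20 March | 1 | 20 March, Day 1 |
| 28 March | min(20, 28) = 20: 20 March | 1 | 20 March, Day 1 |
| 5 April | min(20, 5) = 5: 5 March | 5 - 20 = -15 | 20 March, Day 1 |
| 19 April | min(20, 19) = 19: 19 March | 19 - 20 = -1 | 20 March, Day 1 |
| 25 April | min(20, 25) = 20: 20 March | 1 | 20 March, Day 1 |

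The error needs an end date in a later month with a smaller day number than the dosing day. By the month rule, the 5 April event is treatment-emergent with an onset 15 days before treatment. That onset also precedes consent: Protocol Section 3.3 gives screening and baseline less than one day, and Protocol Section 8.7 starts AE reporting at consent.

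**How many date combinations are exposed.** I listed every treatment date in 2021-2022 with every pair of AE start and end on or after treatment, and kept starts in the treatment month.

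- 30-day window: 231,572 combinations, of which 107,822 end in a later month. Item 1a dates 106,198 of these before treatment (106,198/107,822 = 98.5%).
- 37-day window: 113,878 of 187,720 (60.7%). The share falls because more events end late enough to reach the dosing day number again.
- The shift averages 8.6 days (30-day window) or 8.3 days (37-day window), and reaches 30 days in both.
- Comparing full dates leaves 0 of 231,572 before treatment.
- Item 1b (01 in a later month) gives 0 of 107,878 before treatment in the 30-day window, so it needs no change.

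These are shares of possible dates at equal weight, which is an assumption. They are not expected event rates.

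**Anticoagulant restart, if the medication rule is used.** Restart time = restart date - first treatment date + 1.

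- Restart in March, day missing: 1 March, so (1 - 20) + 1 = -18.
- Only the year known: 1 January 2022, 78 days before 20 March, so -78 + 1 = -77.
- Restart in the treatment month, day missing, over all 730 treatment dates: the imputed date precedes treatment unless treatment was on the 1st. That is (730 - 24)/730 = 96.7%, with mean restart time -13.7 and minimum -29.
- With a floor at treatment start, both examples give (20 - 20) + 1 = 1.

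**The case against.** Much of the case on the other side stands.

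- **Classification is protected.** Treatment-emergent status and the prior/concomitant flag do not use the imputed day. The AE tables in SAP Section 5.7.2 are counts by class, term, relationship and severity; none is specified by onset day.
- **The link to anticoagulants is an inference.** Restart dates go on a dedicated CRF (Protocol Appendix A, footnote 12), and Protocol Section 7.2.1 asks for date, time and agent. The SAP does not say that restart time uses the concomitant medication imputation. Restarted anticoagulants are, however, concomitant medications, and no other rule is offered.
- **Partial dates may be few** in a study of about 30 days with repeated contacts. A restart with only the year known would be unusual.
- **Item 1a might mean calendar dates.** The AE error would then vanish. But the text says day, and the result is used to fill a missing day.

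A reader might infer that these rules bias the safety table with the category "Used anticoagulants before the first TE" (SAP Section 5.7.2.6), and that correcting them would repair it. The documents do not support that. Take dosing on 20 March, a thrombotic event on 25 March and a restart in March with the day unknown. The SAP rule gives 1 March and a floored rule gives 20 March; both precede the event. A restart in a later month is put on the 1st of that month with or without a floor, and stays after an event in an earlier month. An event dated too early moves ahead of a restart, the opposite direction from a restart dated too early. Only same-day ties, or participants with both dates partial, could change category. The SAP also does not say that this table uses imputed dates.

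**Conclusion.** Both rules are wrong as written, with low severity. Item 1a can give a treatment-emergent event an onset before treatment, by up to 30 days. The medication rule, if it governs restarts, gives restart times that cannot occur, such as -18. No other section of the SAP or protocol corrects either.

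The damage is confined to records with a partial date. For AEs it is further confined to those starting in the dosing month and ending in a later month on a smaller day number. It affects onset day, any duration derived from it, and time to restart. It does not affect treatment-emergent counts, the concomitant flag or the primary endpoint, and correcting it would not materially change the table of anticoagulant use before or after the first thrombotic event. Because the number of partial dates is not given, no expected count of affected participants can be stated. The restart part also rests on the assumption that the concomitant medication rule applies to restarts.

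**What to change.** - **AE item 1a only.** When the recorded start month and year match those of first treatment, impute the start as the earlier of the first study treatment date and the AE end date, comparing full dates. If the end date is missing, use the treatment date. Leave item 1b as it is. Where start and end share a month the result is the same as now, so only the faulty case changes.
- **Anticoagulants recorded as restarted after treatment.** State which rule applies. Impute a missing day as the later of the first of the recorded month and the start of study treatment (the randomization date for usual care with no treatment, as the SAP already defines it). If the month is also missing and the year is the treatment year, use the start of study treatment. In each case the imputed date must not fall after the recorded stop date.

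The cost is two SAP sentences and one date function. No new data are needed.

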6.2. Appendix 2: Study and Participant Characteristics

Summaries that are presented as the Table 14.1 or Table 14.3 series, which are not described in the body of the SAP are provided here.

6.2.1. **Protocol Deviations**

Protocol deviations will be tabulated by treatment group and total. By-participant listings of protocol deviation data will be provided. For details, please refer to the protocol deviation review plan.

6.2.2. Demographics and Disease Characteristics

Baseline and demographic characteristics will be summarized by treatment group.

By-participant listings of demographics, baseline characteristics, initial bleeding events, events leading to randomization, medical/surgical history, and prior/concomitant medications will be provided.

6.2.2.1. Demographics and Disease Characteristics (Bleeding)

The following demographic and baseline disease characteristics variables will be summarized by treatment group and total using descriptive statistics. No inferential analyses of these data are planned.

• Sex (male or female).

- Race (American Indian or Alaska native, Asian, Black or African American, Native Hawaiian or other pacific islander, White, or other).
- Ethnicity (Hispanic or Latino, not Hispanic Or Latino, not reported, or unknown).
- Age (< 65 years, 65 to 74 years, or \geq 75 years).
- Height (cm).
- Weight (kg).
- Body mass index (< 25 kg/m², 25 to < 30 kg/m², or \ge 30 kg/m²).
- Tobacco use (current, former, or never).
- Geographic region (North America, Europe, or Asia).
- FXa inhibitor (apixaban, edoxaban, or rivaroxaban).
- Indication of FXa inhibitor (atrial fibrillation, venous thromboembolism, or other).
- Intended UC agent: PCC, other
- Time since the last FXa inhibitor dose to scan for bleeding (< 180 minutes versus \geq 180 minutes).
- Baseline anti-fXa activity (< 30 to \ge 30 ng/mL and < 75 to \ge 75 ng/mL).
- Participant presentation location (emergency room/department, ICU, inpatient ward, stroke clinic, transfer from outside hospital, or other).
- Approximate hematoma volume of baseline CT/MRI (< 30 and \ge 30 mL; < 0.5 and \ge 0.5 mL).
- Mechanism of injury (spontaneous ICrH and trauma ICrH); participants who will not have bleeding as a result of trauma will be considered as spontaneous bleeding.
- Time from hospitalization to study treatment.
- Time from the last FXa inhibitor dose to treatment (< 8 or \ge 8 hours).
- Time from symptom onset to baseline CT or MRI scan (< 180 minutes versus ≥ 180 minutes).
- Time from CT or MRI scan to treatment.
- Time from bleeding to treatment onset.
- Primary bleeding location per adjudication (intracerebral hemorrhage, not intracerebral hemorrhage, and multicompartment, where intracerebral hemorrhage includes intracerebral or intraventricular bleeding, and not intracerebral hemorrhage includes subdural or subarachnoid bleeding).
- Intracerebral hemorrhage (ICH) score (< 3 or \geq 3).

6.2.2.2. Medical/Surgical History and Baseline Physical Examination

The number of participants with any medical history will be tabulated by treatment group and total. The number of participants with at least 1 medical history will also be tabulated by SOC and PT; if participants experienced > 1 history in a specific SOC or PT, they will be counted only once for the SOC or PT.

6.2.3. Prior and Concomitant Medications

Prior medications are defined as medications that are started prior to the start of study treatment, as defined in Section 6.1.

Concomitant medications are defined as medications that are started on or after the start of study treatment or are ongoing at the start of study treatment. Prior medications with missing end dates will be counted as concomitant.

The number of participants with any prior and concomitant medications will be tabulated by treatment group and total. The number of participants with at least 1 prior and 1 concomitant medications will also be tabulated by Anatomical Therapeutic Chemical 3 Classification and by generic name. All prior and concomitant medications will be listed and summarized by treatment group for the Safety Set.

In addition, the number of participants of concomitant anticoagulants and antiplatelet drugs will be tabulated by treatment group and total.

6.3. Appendix 3: Instrument Scoring Details

6.3.1. Glasgow Coma Scale

In order to provide a total summary score for the GCS, data coded as "untestable" for the verbal response question will be coded as follows based on the combination score of eye and motor (EM) scores (Brennan, 2020):

- If the EM scores are 2 to 6, then add 1.
- If the EM score is 7, then add 2.
- If the EM score is 8 or 9, then add 4.
- If the EM score is 10, then add 5.

6.3.2. Utility-Weighted mRS

The determination of utility weights for the mRS will be determined as follows:

- mRS utilities represent preferences for mRS health states and range from < 1 to 1 (perfect health), where 0 indicates death.
- Utility values for each mRS health data will be elicited using the EQ-5D-5L responses of participant or proxy assessed at 30 days post-randomization (Chaisinanunkul, 2015). The EQ-5D-5L consists of 5 dimensions (mobility, self-care, usual activities, pain/discomfort, and anxiety/depression) with 5 levels each (no

problems, slight problems, moderate problems, severe problems, and unable to/extreme problems), thus defining 3125 distinct health states.

- Converting the EQ-5D-5L responses into EQ-5D utility values was done according to Table 7 below. Participants who died before the follow-up interviews at 30 days will receive a utility value of 0. The utility values range from < 0 (where 0 is the value of a health state equivalent to dead, and negative values represent values as worse than dead) to 1 (full health).
- The utility weights for each mRS category (1 to 5, excluding 6 which is death) will be determined by averaging the derived EQ-5D utilities of all participants within each of the mRS health states (eg, the utility weight for mRS = 1 is the average of the utilities of all participants with mRS = 1).
- The utility weights as derived above will be used in analyses.

6.3.3. EQ-5D-5L Health State Index Score Calculations

The responses to the 5 EQ-5D dimensions can be converted into a single number called an index value. The EQ-5D-5L health state index score is derived by applying a formula that attaches values (also called weights) to each of the levels in each dimension. The index can be calculated by subtracting the appropriate weights for each dimension level of health state from 1. The EQ-5D-5L index scores for this study will be obtained using the US composite time trade-off method (Pickard, 2019; Mehta, 2011). The calculation is illustrated in below (Pickard, 2019):

US cTTO		Example: The value for health state is 21354
Full health (11111)		Full health $= 1$
Mobility Level 2	-0.096	-0.096
Mobility Level 3	-0.122	
Mobility Level 4	-0.237	
Mobility Level 5	-0.322	
Self-care Level 2	-0.089	0
Self-care Level 3	-0.107	
Self-care Level 4	-0.220	
Self-care Level 5	-0.261	
Usual activity Level 2	-0.068	
Usual activity Level 3	-0.101	-0.101

Table 7:EQ-5D-5L US cTTO Value Set

US cTTO		Example: The value for health state is 21354
Usual activity Level 4	-0.255	
Usual activity Level 5	-0.255	
Pain/discomfort Level 2	-0.06	
Pain/discomfort Level 3	-0.098	
Pain/discomfort Level 4	-0.318	
Pain/discomfort Level 5	-0.414	-0.414
Anxiety/depression Level 2	-0.057	
Anxiety/depression Level 3	-0.123	
Anxiety/depression Level 4	-0.299	-0.299
Anxiety/depression Level 5	-0.321	
Health state index score		=1 - 0.096 + 0 - 0.101 - 0.414 - 0.299 = 0.090

Table 7:EQ-5D-5L US cTTO Value Set

Abbreviation: cTTO = composite time trade-off; EQ-5D-5L = European Quality of Life 5-Dimension 5-Level; US = United States

6.4. Appendix 4: Additional Details on Statistical Methods

6.4.1. COVID-19 Vaccine Risk Assessment

6.4.1.1. Vaccination

Following a review of the available coronavirus disease 2019 (COVID-19) vaccine data (eg, Pfizer/BioNTech, Moderna, AstraZeneca, and Johnson & Johnson), it is unlikely that the immune response to a COVID-19 vaccine (and therefore the efficacy of the vaccination) would be diminished with concomitant administration of andexanet, based on andexanet's mechanism of action. There is currently no available information evaluating the safety and efficacy of COVID-19 vaccines in participants treated with andexanet.

